### **10.6 OBLIGATION OF THE INVESTIGATOR REGARDING SAFETY REPORTING**

#### **10.6.1 Definitions of adverse events**

##### **10.6.1.1 Adverse event**

An AE is any untoward medical occurrence in a patient or clinical investigation patient administered a pharmaceutical product and which does not necessarily have to have a causal relationship with this treatment.

#### **10.6.1.2 Serious adverse event**

An SAE is any untoward medical occurrence that at any dose:

- Results in death, or
- Is life-threatening, or

Note: The term “life-threatening” in the definition of “serious” refers to an event in which the patient was at risk of death at the time of the event; it does not refer to an event which hypothetically might have caused death if it were more severe.

- Requires inpatient hospitalization or prolongation of existing hospitalization, or
- Results in persistent or significant disability/incapacity, or
- Is a congenital anomaly/birth defect
- Is a medically important event

Medical and scientific judgment should be exercised in deciding whether expedited reporting is appropriate in other situations, such as important medical events that may not be immediately life-threatening or result in death or hospitalization but may jeopardize the patient or may require medical or surgical intervention (ie, specific measures or corrective treatment) to prevent one of the other outcomes listed in the definition above.

Note: The following list of medically important events is intended to serve as a guideline for determining which condition has to be considered as a medically important event. The list is not intended to be exhaustive:

- Intensive treatment in an emergency room or at home for:
  - a) Allergic bronchospasm,
  - b) Blood dyscrasias (ie, agranulocytosis, aplastic anemia, bone marrow aplasia, myelodysplasia, pancytopenia, etc),
  - c) Convulsions (seizures, epilepsy, epileptic fit, absence, etc).
- Development of drug dependence or drug abuse
- Suicide attempt or any event suggestive of suicidality
- Syncope, loss of consciousness (except if documented as a consequence of blood sampling)
- Bullous cutaneous eruptions
- Cancers diagnosed during the study or aggravated during the study (only if judged unusual/significant by the investigators in oncology studies)
- Chronic neurodegenerative diseases (newly diagnosed) or aggravated during the study (only if judged unusual/significant by the investigators).

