### 7.2 EXCLUSION CRITERIA

Patients who have met all the inclusion criteria listed in [Section 7.1](#) will be screened for the following exclusion criteria:

- E 01. The patient has received an investigational drug within the 30 days before study enrollment.
- E 02. The patient has any of the following medical conditions:
  - a) An active, serious, intercurrent illness;
  - b) Active hepatitis B or hepatitis C infection;

- c) Infection with human immunodeficiency virus (HIV);
- d) Cirrhosis (determined by clinical evaluation);
- e) Significant cardiac disease (eg, clinically significant arrhythmia, moderate or severe pulmonary hypertension or valvular dysfunction, or <40% left ventricular ejection fraction by echocardiogram);
- f) Malignancy diagnosed within the previous 5 years (except basal cell carcinoma);
- g) Any other extenuating circumstance that can significantly interfere with study compliance, including all prescribed evaluations and follow-up activities.

- E 03. The patient has acute or rapidly progressive neurological abnormalities.
- E 04. The patient is homozygous for *SMPD1* gene mutations R496L, L302P, and fs330 or any combination of these 3 mutations.
- E 05. The patient has delayed gross motor skills.
- E 06. The patient has had a major organ transplant (eg, bone marrow, liver).
- E 07. The patient requires use of invasive ventilatory support.
- E 08. The patient requires use of noninvasive ventilatory support while awake and for >12 hours a day.
- E 09. The patient, in the investigator's opinion, is unable to adhere to the requirements of the study.
- E 10. The patient has a platelet count <60 × 10^3/µL (based on the average of 2 screening samples obtained greater than 24 hours apart).
- E 11. The patient has alanine aminotransferase or aspartate aminotransferase >250 IU/L or total bilirubin >1.5 mg/dL.
- E 12. The patient has an international normalized ratio (INR) >1.5.
- E 13. The patient is unwilling or unable to abstain from ingesting alcohol the day before through 3 days after each infusion of olipudase alfa during the treatment period. Measuring alcohol concentration in blood is not required.
- E 14. The patient is scheduled during the study for in-patient hospitalization including elective surgery.
- E 15. The patient requires medication(s) that may decrease olipudase alfa activity (eg, fluoxetine, chlorpromazine; tricyclic antidepressants [eg, imipramine, or desipramine]).
- E 16. The patient is breast-feeding.

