#### ***8.3.4.2.1 Dose limiting toxicity patient stopping criteria***

If any of the following AEs occur, dosing will be temporarily stopped for the specific patient who experienced the AE:

- Any SAE, not related to the patient's underlying condition and considered related to the study treatment.
- Any increase in aspartate aminotransferase (AST), alanine aminotransferase (ALT), total bilirubin, or alkaline phosphatase (AP)  $>3$ x baseline (prior to olipudase alfa therapy) and  $>$  the upper limit of normal (ULN).
- Any increase in total bilirubin or AP  $>1.5$ x baseline, in the presence of AST or ALT  $>2$ x ULN.
- Any increase in ALT or AST  $>3$ x the ULN combined with an increase in ALT or AST  $>2$ x baseline (prior to olipudase alfa therapy) with symptoms of fatigue, nausea, vomiting, fever, rash, or eosinophilia ( $>$ ULN).
- Any AE that, in the opinion of the investigator or sponsor, raises significant concern regarding the safety of olipudase alfa at the administered dose.

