The study investigator must score all abnormal laboratory values as either CS or NCS. Because some laboratory values may be outside of the normal value range due to the underlying disease, the study investigators should use clinical judgment when considering clinical significance. Clinical significance is defined as any change in laboratory parameters from baseline, which has medical relevance. If CS worsening of laboratory values from screening levels is noted, the changes will be documented as an AE and scored per [Section 10.6.1.4.3](#). The study investigator will continue to monitor the patient with additional laboratory assessments until (1) values have reached normal range and/or screening levels, or, (2) in the judgment of the study investigator, abnormal values are not related to the administration of IMP or other protocol-specific procedures.

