#### **10.6.2 General guidelines for reporting adverse events**

- All AEs, regardless of seriousness or relationship to IMP/NIMP, spanning from the signature of the informed consent form until the end of the study as defined by the protocol for that patient, are to be recorded on the corresponding page(s) or screen(s) of the e-CRF.
- Except for IARs, whenever possible, diagnosis or single syndrome should be reported instead of symptoms. For IARs, all symptoms must be separately recorded.
- The investigator should specify the date of onset, intensity, action taken with respect to IMP, corrective treatment/therapy given, additional investigations performed, outcome, and his/her opinion as to whether there is a reasonable possibility that the AE was caused by the IMP.
- The investigator should take appropriate measures to follow all AEs until clinical recovery is complete and laboratory results have returned to normal, or until progression has been stabilized, or until death, in order to ensure the safety of the patients.
- When treatment is prematurely discontinued, the patient's observations will continue until the end of the study as defined by the protocol.
- Laboratory, vital signs or ECG abnormalities are to be recorded as AEs only if:
  - Symptomatic and/or
  - Requiring either corrective treatment or consultation, and/or
  - Leading to IMP discontinuation or modification of dosing, and/or
  - Fulfilling a seriousness criterion, and/or
  - Defined as an AESI (see [Section 10.6.1.3](#))

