**Table 8 - Summary of adverse event reporting instructions**

EVENT CATEGORY	REPORTING TIMEFRAME	SPECIFIC EVENTS IN THIS CATEGORY	CASE REPORT FORM COMPLETION		
			AE form	Safety Complementary Form	Other specific forms
Adverse Event (non-SAE, non-AESI)	Routine	Any AE that is not SAE or AESI	Yes	No	No
Serious Adverse Event (non-AESI or AESI)	Expedited (within 24 hours)	Any AE meeting seriousness criterion per Section 10.6.1.2 ALT $\geq$ 3 ULN	Yes	Yes	No
Adverse Event of Special Interest	Expedited (within 24 hours)	Symptomatic overdose  Infusion associated reactions (IAR)/Hypersensitivity reactions  Pregnancy	Yes  Yes  Yes	Yes  Yes  Yes	No  Yes  Yes

AE: adverse event; AESI: adverse event of special interest; SAE: serious adverse event; ULN: upper limit of normal

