Laboratory values: The following protocol-defined potential dose limiting toxicities are also considered AESIs:

- Any increase in AST, ALT, total bilirubin, or AP $>3x$ baseline (before olipudase alfa therapy) and $>$ ULN;
- Any increase in total bilirubin or AP $>1.5x$ baseline, in the presence of AST or ALT $>2x$ ULN;
- Any increase in ALT or AST $>3x$ ULN combined with an increase in ALT or AST $>2x$ baseline (prior to olipudase alfa therapy), with symptoms of fatigue, nausea, vomiting, fever, rash, or eosinophilia ($>$ ULN).

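### Protocol Table 8 puts ALT ≥ 3 ULN in the SAE row, in conflict with the SAE definition and the baseline-related liver rules, so a modest treatment-related rise from a high baseline could be handled as an SAE and potential DLT

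*Protocol*

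**What the plan says.** **SAE definition (Protocol 10.6.1.2).** "An SAE is any untoward medical occurrence that at any dose" meets one of six criteria: death, threat to life, hospitalization, disability, congenital anomaly, or medical importance. The examples of medical importance contain no ALT or other laboratory level, although "The list is not intended to be exhaustive".

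**Summary of reporting (Protocol Table 8).** The SAE row, reportable within 24 hours, has two items: any AE that meets a criterion of 10.6.1.2, and ALT ≥ 3 ULN with no baseline condition. The AESI row lists symptomatic overdose, infusion reactions and pregnancy, and no liver criterion.

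**Liver rules in the text.** Protocol 10.6.4.1 (AESI), Protocol 8.3.4.2.1 (patient stopping criteria) and SAP 2.6.1.3 give the same three rules:
- Rule 1: "Any increase in AST, ALT, total bilirubin, or AP $>3x$ baseline (before olipudase alfa therapy) and $>$ ULN".
- Rule 2: bilirubin or AP above 1.5 times baseline while AST or ALT is above 2 ULN.
- Rule 3: ALT or AST above 3 ULN and also above 2 times baseline, with listed symptoms or eosinophilia.

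**Entry (Protocol 7.2, E 11).** A child is excluded if "The patient has alanine aminotransferase or aspartate aminotransferase >250 IU/L or total bilirubin >1.5 mg/dL".

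**Dosing stop (Protocol 8.3.4.2.1).** The SAE criterion is "Any SAE, not related to the patient's underlying condition and considered related to the study treatment".

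**When a laboratory value is an AE.** Protocol 9.1.8: "If CS worsening of laboratory values from screening levels is noted, the changes will be documented as an AE". Protocol 10.6.2: "Laboratory, vital signs or ECG abnormalities are to be recorded as AEs only if" at least one of five conditions holds, among them a seriousness criterion or AESI status.

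**The concern.** Table 8 is the page a site is likely to use when deciding what to report within a day. It contains an SAE trigger that the definition it cites does not contain, and it leaves out the three liver triggers that the text does require.

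SAEs belong to the primary safety endpoint. They are tabulated (SAP 2.6.1.5) and each needs a narrative (SAP 2.10). An SAE that meets both conditions of the stopping criterion is a potential DLT. Under Protocol 8.3.4.2 that means a temporary stop, DMC review, written notice to the ethics committee, and resumption at the previously tolerated lower dose once the event has reversed.

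Two sites with the same ALT value could therefore act differently. One that follows Table 8 reports an SAE and, if the rise is judged related to treatment and not to the disease, holds dosing. One that follows 10.6.1.2 and 8.3.4.2.1 does neither.

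The omission works the other way. A site relying on Table 8 could miss a liver AESI, including a bilirubin rise. Protocol 4.1 reports that the Phase 1 study was terminated after a patient developed hyperbilirubinemia with an acute-phase reaction.

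**Working it through.** The plan states no figure to reproduce; this is a comparison of thresholds.

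**Inputs.** Entry limit for ALT: 250 IU/L (E 11). Table 8 level: 3 ULN. Text rules on ALT: more than 3 times baseline and above ULN (rule 1); more than 3 ULN and more than 2 times baseline, with symptoms (rule 3). The documents give no ALT ULN, so I assume 40 IU/L, with a range of 25 to 60 IU/L.

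**1. Can an eligible child be at the Table 8 level before dosing?** This needs 3 ULN ≤ 250, that is ULN ≤ 250/3 = 83.3 IU/L. Over 25 to 60 IU/L, 3 ULN is 75 to 180 IU/L, and the entry limit is 250/25 = 10.0 to 250/60 = 4.2 ULN. So the answer is yes across the whole range.

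**2. Where do the thresholds fall?** With ULN 40, Table 8 is met at 3 × 40 = 120 IU/L.

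| Baseline ALT (IU/L) | Table 8 level as multiple of baseline | Rule 1 (IU/L) | Rule 3, with symptoms (IU/L) |
|---|---|---|---|
| 20 | 120/20 = 6.0 | > 60 | > 120 |
| 100 | 120/100 = 1.2 | > 300 | > 200 |
| 120 | 120/120 = 1.0 | > 360 | > 240 |
| 250 | already exceeded | > 750 | > 500 |

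**3. Does this depend on the assumed ULN?** The direction does not. Write B for baseline ALT. Then 3 ULN < 3B whenever B > ULN, and 3 ULN < 2B whenever B > 1.5 ULN. Table 8 is thus easier to meet than rule 1 for every child whose baseline is above normal, and harder for every child whose baseline is below the ULN. The baseline of 20 shows the second case: rule 1 applies above 60 IU/L, while the ALT item in Table 8 is silent until 120 IU/L. For a baseline of 100 IU/L, a ULN of 50 gives 150/100 = 1.5 times baseline and a ULN of 60 gives 1.8 times. At a ULN of 30 (level 90 IU/L) the child is already above the level at entry. Rules 1 and 3 stay at > 300 and > 200 IU/L throughout.

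**4. Rule 2.** It has no baseline term for ALT, but it needs a bilirubin or AP rise above 1.5 times baseline. An isolated ALT rise does not meet it.

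**5. Opportunities and weight.** Protocol Tables 4 to 6 plan about 43, 30 and 29 liver function samples per patient in the treatment period, by age group. With 20 patients, one patient with a laboratory-only SAE moves the overall SAE percentage by 1/20 = 5 points.

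**The case against.** **A child could seem to have an SAE at the entry value.** A reader might infer this from step 1. The documents do not support it. An SAE must first be an adverse event, and 9.1.8 requires clinically significant worsening from screening. The seriousness route in 10.6.2 captures an unchanged value only if Table 8 is already assumed to have added a criterion. A value present before the first infusion would also fall outside the SAE table in SAP 2.6.1.5, which covers treatment-emergent events.

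**Any related SAE could seem to stop dosing.** It does not. The criterion also requires that the SAE not be due to the underlying condition, so a stable disease-related ALT stops nothing. The stop is temporary.

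**ULN-based liver flags are part of this plan.** This is correct. The liver listing in Protocol 11.4.2.2 and the PCSA limits in SAP 2.11.5 use ULN multiples, and so does the ALT part of rule 2. The conflict is confined to the AESI and stopping rules, each of which has a baseline term somewhere.

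**The analysis definition is settled.** Protocol 11.4.2.1 and SAP 2.6.1.1 point to the definitions in 10.6.1, and Table 8 lies outside that section. This narrows the point. But the SAE table counts what sites record as serious, and that reference does not tell the analyst how to treat a report made on the strength of Table 8.

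**The list of medically important events is open.** Table 8 could be read as adding an example. However, 10.6.1.2 asks for medical judgment, whereas Table 8 gives a bare cut-off.

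**The row placement may come from reading the PDF.** The SAE row has two items but one set of form entries, so a displaced cell cannot be excluded. The AESI row has three events matched by three sets, which favors the SAE reading. If the item belongs in the AESI row, the SAE and DLT consequences fall away. It still conflicts with 10.6.4.1, which has no plain ALT ≥ 3 ULN criterion.

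**Conclusion.** The point holds as an inconsistency in the reporting threshold. Followed as written, Table 8 allows a modest ALT rise from a high baseline to be reported as an SAE. If the rise is judged related to treatment and not to the disease, it is then handled as a potential DLT. With a ULN of 40 IU/L and a baseline of 100 IU/L, that happens at 1.2 times baseline, against more than 3 times, or more than 2 times with symptoms, in the text.

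This rests on three conditions: the item is in the SAE row, the site accepts the rise as an adverse event, and the site acts on Table 8. The ULN is assumed, but the ordering of the thresholds for any baseline above normal is not. The documents do not show how many children would be affected. The omission of the three liver criteria from Table 8 depends on none of these conditions. It does not repeal 10.6.4.1, but it leaves the summary incomplete.

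**What to change.** **Protocol Table 8.** Delete ALT ≥ 3 ULN from the SAE row and list the three liver criteria of 10.6.4.1 in the AESI row. One set of liver rules then serves reporting and stopping.

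**SAP 2.6.1.5.** Base the SAE table on the seriousness criterion recorded under Protocol 10.6.1.2; SAP 2.6.1.1 shows that the e-CRF holds this field. Show any report whose only basis is ALT ≥ 3 ULN on a separate line, with the baseline ALT and the multiple of baseline reached.

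**Cost.** One table edit, one SAP sentence and one extra output line. Little is lost: an isolated ALT above 3 ULN is still captured by the PCSA summaries in SAP 2.6.5 and 2.11.5.

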### **10.6.1.3 Adverse event of special interest**

An AESI is an AE (serious or non-serious) of scientific and medical concern specific to the sponsor's product or program, for which ongoing monitoring and rapid communication by the investigator to the sponsor may be appropriate. Such events may require further investigation in order to characterize and understand them. Adverse events of special interest may be added or removed during a study by protocol amendment.

AESIs include the following:

#### **10.6.1.3.1 Pregnancy**

Pregnancy of a female patient entered in the study as well as pregnancy occurring in female partner of a male patient enrolled in this study. See [Section 10.7](#) for additional details.

#### **10.6.1.3.2 Infusion-associated reactions**

Some AEs may be manifestations of IARs, including hypersensitivity reaction, acute phase reactions (APR), and cytokine release syndrome (CRS), as described in [Section 10.6.1.3.2.1](#), [Section 10.6.1.3.2.2](#), and [Section 10.6.1.3.2.3](#), respectively. However, original signs and symptoms must be reported as AEs. In the e-CRF, investigators are asked to identify whether a specific AE represents a clinical manifestation of the IAR.

Infusion-associated reactions are defined as AEs that occur during the infusion or within up to 24 hours after the start of infusion and are considered as related or possibly related to the study treatment by the investigator or the sponsor. An event occurring  $\geq 24$  hours after the start of an infusion may be judged an IAR at the discretion of the investigator or sponsor. For this study of olipudase alfa, IARs may present as different types of reactions, such as hypersensitivity reactions, APRs, and CRS.

##### **10.6.1.3.2.1 Hypersensitivity reactions**

Infusion-associated hypersensitivity reactions seen with other enzyme replacement therapies are typically immunoglobulin-mediated (IgG/IgE) and occur after sensitization. After subsequent exposure to the antigen typically early into or shortly after the infusion, a "sensitized" patient may experience a broad range of allergic reactions that can be mild to severe or life threatening. Anaphylaxis (or anaphylactic reaction) is a serious, IgE mediated allergic reaction that is rapid in onset, and may cause death (15). Anaphylactoid, or non-immunologic anaphylaxis, reactions may present with similar serious clinical manifestations as anaphylaxis, but without prior exposure to the drug and are due to nonimmunologic-mediated mast cell degranulation. Although mechanistically different, anaphylactic and anaphylactoid reactions are treated similarly.

Common symptoms of hypersensitivity reactions seen with other enzyme replacement therapy include urticaria, rash, dyspnea, and less frequently, angioedema. Other symptoms of hypersensitivity IARs, APRs and CRS include fever, hypotension, tachycardia, nausea, vomiting, pain, and headache.

There were no IAR suggestive of hypersensitivity in the Phase 1b trial (6).

#### 10.6.1.3.2.2 Acute phase reactions

Acute phase reactions observed in the phase 1 and phase 1b studies are considered as one type of IAR, specific to the infused olipudase alfa therapy (5, 6). From observations in both studies the APR reactions typically occurred within 12-72 hours following an infusion of olipudase alfa and were indicative of an inflammatory response. APRs were associated with elevations in hsCRP and changes acute phase reactants including, but not limited to, neutrophils, iron, ferritin, fibrinogen, D-dimer, transferrin, albumin, protime, and partial thromboplastin time. Patient AEs associated with the APR included (but are not limited to) pyrexia, nausea, vomiting, fatigue, and pain. Acute phase reaction is determined based on combined significant laboratory findings and clinical symptoms.

#### 10.6.1.3.2.3 Cytokine release syndrome

Cytokine release syndrome is another type of IAR, attributed to the release of excessive amounts of cytokines shortly after the intravenous administration of certain therapeutic agents. The severe form of CRS is a cytokine storm, which may be life threatening. Nonclinical studies of high-dose olipudase alfa have suggested the possibility of cytokine release syndrome. The Phase 1 single dose study (5) demonstrated increases in IL-8 and IL-6; macrophage inflammatory protein 1, alpha component; macrophage inflammatory protein 1, beta component; and other cytokines and biomarkers (based Myriad Rules-Based Medicine Human Multi-Analyte Profile® antigen panel) after a single dose of  $\geq 0.3$  mg/kg olipudase alfa. In the Phase 1b trial, increases in mean IL-6 and IL-8 values were associated with the first administrations of olipudase alfa at doses 0.6 mg/kg through 2.0 mg/kg and tended to be concurrent with acute phase responses (6). Unlike immunoglobulin-mediated hypersensitivity reactions, no prior antigen exposure is required for the development of CRS. Symptoms of CRS develop soon after exposure, and range from mild to severe. Although CRS shares some symptoms with other IARs (ie, hypersensitivity reactions and APRs), symptoms typical of CRS include pyrexia, nausea, vomiting, fatigue, pain, myalgia, and in severe cases, multi-organ system dysfunction or failure, severe headache, and pulmonary edema. Cytokine release syndrome is determined based on combined significant laboratory findings and clinical symptoms.

